5.1.2 Part 2 IPdR Dose Escalation Schedule

Original Design (no longer active, reference only): In Part 2 of this Phase 1 protocol, a standard cohort 3+3 design (see table 5) will be used where up to three patients will be accrued to a given dose level (starting with no increase of the final Part 1 dose and escalating per table 6). After each cohort has been accrued the study will temporarily close to assess DLT status of each patient. The decisions to re-open, and at what level to re-open, are on the following:

- If DLT is not seen in any of the 3 patients, 3 new patients will be accrued and treated at the next higher dose level. If DLT is seen in 2 or 3 of 3 patients treated at a given dose level, then the MTD has been exceeded and the next 3 patients will be treated at the next lower dose level (unless there have already been 6 accrued to that lower level).
- If DLT is seen in 1 of 3 patients treated at a given dose level, up to 3 additional patients will be enrolled and treated at the same dose level. If DLT is seen in at least one of these additional patients (at least 2 of 6), the MTD will have been exceeded. If DLT is not seen in any of the three additional patients, 3 new patients will be accrued and treated at the next higher dose level.
- After enrolling 6 patients on a specific dose level, if DLT is observed in at least 2 of 6 patients, then the MTD will have been exceeded and defined as the previous dose level unless only 3 patients were treated at the lower dose level. In that case, 3 additional patients will be treated at this lower dose level such that a total of 6 patients are treated at the MTD to more fully assess the toxicities associated with the MTD.
- If a patient fails to complete the initial course of therapy (cycle 1) for reasons other than dose-limiting toxicity defined adverse events, the patient will be regarded as uninformative in regard to the MTD goal and an additional patient will be treated at the current dose level; however, all toxicity information will be utilized in the analysis.

The MTD is defined as the dose below which 2 or more of 6 patients experience dose-limiting toxicity.

Design Amendment #1 (to be superceded by Design amendment #2 below):

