In Part 2 of this Phase 1 protocol, a modified cohort 3+3 design (see table 5) will be used where up to three patients will be accrued to a given dose level (starting with 1200 mg IPdR dose and escalating per table 6). After each cohort has been accrued the study will temporarily close to assess DLT status of each patient. The decisions to re-open, and at what level to re-open, are on the following:

- If DLT is not seen in any of the 3 patients, 3 new patients will be accrued and treated at the next higher dose level.
- If DLT is seen in 3 of 3 patients treated at a given dose level, then the maximally tolerated dose (MTD) has been exceeded and the next 3 patients will be treated at the next lower dose level such that a total of 6 patients are

treated to more fully assess the toxicities (unless there have already been 6 accrued to that lower level which will then be labeled as the MTD and the study will proceed to the expansion cohort).

- If DLT is seen in 1 or 2 of 3 patients treated at a given dose level, up to 3 additional patients will be enrolled and treated at the same dose level. Including the three additional patients, following rule will be applied:
 - DLT is seen in 1 of the total 6 patients, proceed to the next higher dose level.
 - DLT is seen in 2 of the total 6 patients, then dose escalation is stopped, and this dose level is declared the MTD. The study will proceed to the expansion phase.
 - DLT is seen in 3 or more of the 6 patients have DLT, the MTD will have been exceeded and the next 3 patients will be treated at the next lower dose level such that a total of 6 patients are treated to more fully assess the toxicities (unless there have already been 6 accrued to that lower level which will then be labeled as the MTD and the study will proceed to the expansion cohort).
- If a patient fails to complete the initial course of therapy (cycle 1) for reasons other than dose-limiting toxicity defined adverse events, the patient will be regarded as uninformative in regard to the MTD goal and an additional patient will be treated at the current dose level; however, all toxicity information will be utilized in the analysis.
- In the event MTD is exceeded in part 2 at the first dose level (1200mg), the next lower dose of IPdR will be 900 mg. If MTD is exceeded even at 900 mg, then a dose level of 600 mg will be tested. At both these levels, a minimum of 6 patients will be evaluated.

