The MTD is defined as the highest dose that has fewer than 3 (out of 6) patients experiencing dose-limiting toxicity.

Table 5: Part 2 IPdR Dose Increment Schedule

Dose level	Dose (mg)
2A*	1200
2B	1800
2C	2400

* See text in 5.1.2 for the scenario MTD is exceeded at 1200 mg dose.

Table 6: Part 2 Dose Escalation Decision Rules

Number of Patients with DLT at a Given Dose Level	Escalation Decision Rule
0 out of 3	Enter 3 patients at the next dose level. If this is the highest dose-level, then accrue additional 3 patients at the dose-level.
3 out of 3	MTD is exceeded and the dose escalation will be stopped. This dose level will be declared the maximally administered dose (highest dose administered). Three (3) additional patients will be entered at the next lowest dose level such that a total of 6 patients are treated to more fully assess the toxicities (unless there have already been 6 accrued to that lower level which will then be labeled as the MTD and the study will proceed to the expansion cohort).
1 or 2 out of 3	Enter 3 more patients at this dose level. 
• DLT is seen in 1 of the total 6 patients, proceed to the next higher dose level.• DLT is seen in 2 of the total 6 patients, then dose escalation is stopped, and this dose level is declared the maximally tolerated dose (MTD). The study will proceed to the expansion phase.• DLT is seen in 3 or more of the total 6 patients, then MTD is exceeded and the dose escalation is stopped. This dose level is declared maximally administered dose (highest dose administered). Three (3) additional patients will be entered at the next lowest dose level such that a total of 6 patients are treated to more fully assess the toxicities (unless there have already been 6 accrued to that lower level which will then be labeled as the MTD and the study will proceed to the expansion cohort).
≤ 2 out of 6 at highest dose level below the maximally administered dose	This is the maximally tolerated dose, MTD.

Design Amendment #2:

As described in section 2.5.2, after accruing one patient at the dose-level 2B of table 5, the study is being amended to close the dose-level 2B and re-open 2A (1200 mg) to enroll 3 additional patients. The results of 6 total patients at dose-level 2A (1200 mg) will be evaluated per the table 7 below

Table 7: Part 2 Dose Escalation Decision Rules

Number of Patients with DLT at a Given Dose Level	Escalation Decision Rule

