0 out of 3 (0 out of 6 patients)	This dose-level is declared the recommended phase 2 dose (RP2D). The study will proceed to the expansion phase.
1 or 2 out of 3 (total 1 or 2 out of 6 patients)	This dose level is declared the RP2D. The study will proceed to the expansion phase.
3 out of 3 (total 3 out of 6 patients)	MTD is exceeded and the dose level will be declared the maximally administered dose (highest dose administered). Three (3) additional patients will be entered at the next lowest dose level such that a total of 6 patients are treated to more fully assess the toxicities (unless there have already been 6 accrued to that lower level which will then be labeled as the RP2D and the study will proceed to the expansion cohort).

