5.1.3 Expansion Cohort

An expansion cohort of 10 additional patients will be treated at the RP2D to confirm safety and further test the exploratory biomarkers. If after 16 patients have been treated at the RP2D (6 in part 2 and 10 in the expansion cohort), there are at most 5 patients with a DLT (31.25%) then this dose will remain as the RP2D. If there are more than 5, then the next lower dose will be RP2D.

Based on the design proposed, the highest acceptable probability of DLT is 31.25% (5 or less events in 16 patients), with the target expected probability of DLT of 20-30% (of which 18-20% is expected from WBRT alone).

The following table shows some of the operating characteristics for the current design under a number of possible DLT rates. For each given dose, the table displays the likelihood of increasing to the next dose and the probability of having at most 5 patients with DLTs (out of 16). For example, if the true DLT rate is 0.4 for a given dose level, there is only a 31% chance of accruing above that dose level. If on the other hand, the true DLT rate for a given dose is 0.3 (close to target acceptable rate) and if this dose level is determined to be the MTD during the dose finding stage, then there is a 66.6% chance of having 5 or fewer patients with DLT (out of 16).

DLT Rate	Probability of dose escalation	Probability of having at most 5 Patients with DLT (out of 16)
0.1	0.906	0.997
0.2	0.709	0.918

0.3	0.494	0.660
0.4	0.309	0.329
0.5	0.172	0.105
0.6	0.082	0.019

When a patient at any site is undergoing the study treatment or is pending DLT assessment, the PI of the study (or representative) will regularly meet (in person, by teleconference or by email) with the study statistician and the participating site's study team to review any updates regarding potential adverse events being experienced by the study subject from the WBRT (or any other extracranial RT, if applicable). If necessary, clinical inputs from the treating physician and the participating site PI will be obtained to assist in the decision regarding the adverse event being labeled as a DLT.

Unexpected severe late neurologic radiation toxicity or extra-cranial radiation toxicity will be recorded as a secondary end-point. These events will be reviewed by the independent DSMB who will be charged with considering cessation of the trial if the long term/delayed (6 months) \geq grade 3 symptomatic neurotoxicity or other extra-cranial radiation toxicity is $> 20\%$.

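### Section 5.1.3 gives no operating characteristic for the Table 7 gate now in use: its escalation column follows a superseded rule, and its example at a DLT rate of 0.3 puts a condition on an unconditional probability

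*Combined protocol and SAP*

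**What the plan says.** Section 5.1.3 keeps the dose as RP2D if at most 5 of 16 patients (6 from Part 2, 10 from the expansion) have a DLT. It then says: "The following table shows some of the operating characteristics for the current design under a number of possible DLT rates". The table has two result columns for DLT rates 0.1 to 0.6: the probability of escalating, and the probability of at most 5 DLTs in 16. Two examples follow. At 0.4, "there is only a 31% chance of accruing above that dose level". At 0.3, "if this dose level is determined to be the MTD during the dose finding stage, then there is a 66.6% chance of having 5" DLTs at most; the table row for 0.3 shows 0.660.

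Section 5.1.2 sets out three successive designs.

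- **Original design**, marked as no longer active. After one DLT in the first three patients: "If DLT is not seen in any of the three additional patients, 3 new patients will be accrued" at the next level.
- **Design Amendment #1**, marked as to be superseded. Table 6 escalates after 0/3, and otherwise: "DLT is seen in 1 of the total 6 patients, proceed to the next higher dose level". At 2 of 6, "then dose escalation is stopped, and this dose level is declared the MTD".
- **Design Amendment #2**, the rule in force: "the study is being amended to close the dose-level 2B and re-open 2A (1200 mg) to enroll 3 additional patients". The six patients are judged by Table 7, which sends the dose to expansion on 0 of 6 or on "1 or 2 out of 3 (total 1 or 2 out of 6 patients"), and fails it on 3 of 6.

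The Synopsis and Section 2.5.2 report no DLTs in the first three patients at 1200 mg. Section 13.1 makes the RP2D the primary endpoint and refers to 5.1.3 for how it is determined.

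**The concern.** The table is presented as describing the current design, but the current design cannot escalate. If the first column belongs to an older rule, the gate that now decides whether 1200 mg enters expansion has no stated pass probability. The example at 0.3 raises a separate problem: it speaks of a dose already selected in dose finding, yet its figure looks like a plain binomial probability for 16 unselected patients.

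Section 13 gives no error rates of its own, so this table is the only place to judge the risk of keeping a dose that is too toxic. Section 5.1.3 sets the highest acceptable DLT probability at 31.25%, so the rows at 0.4 and above show that risk. The text makes no conditional claim for those rows. A reader who carries the example's condition down to them would nevertheless overrate the protection given by the 5/16 rule.

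**Working it through.** **Inputs.** DLT rate p from the 5.1.3 table; the escalation rules of the original design and of Table 6; the Table 7 gate; 0/3 observed at 1200 mg; the rule of at most 5/16. DLTs are taken as independent with a common rate p. B(k; n, p) is the binomial probability of exactly k events, and F(k; n, p) that of at most k.

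**1. Reproduce the escalation column.** Escalating on 0/3, or on 1/3 then 0/3, has probability (1−p)³ + 3p(1−p)²·(1−p)³ = (1−p)³ + 3p(1−p)⁵.

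At p = 0.3: 0.343 + 0.441 × 0.343 = 0.494. For p = 0.1 to 0.6 the formula gives 0.906, 0.709, 0.494, 0.309, 0.172, 0.082. All six rows match. The original design and Amendment #1 share this rule; Table 7 has no such step.

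**2. Reproduce the last column.** F(5; 16, p) = 0.9967, 0.9183, 0.6598, 0.3288, 0.1051, 0.0191. All six rows match, so the column is unconditional. The 66.6% in the text differs from the exact 0.6598.

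**3. Table 7 for 1200 mg, given 0/3.** The dose fails only on 3/3 new DLTs.

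- Pass = 1 − p³.
- Pass and at most 5/16 = Σ over x = 0, 1, 2 of B(x; 3, p) · F(5−x; 10, p).
- At most 5/16 given a pass = the second divided by the first.

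At p = 0.3: 0.343 × 0.9527 + 0.441 × 0.8497 + 0.189 × 0.6496 = 0.8243, and 0.8243 / 0.973 = 0.8471.

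| p | Pass Table 7 | Pass and ≤5/16 | ≤5/16 given pass | Printed, unconditional |
|---|---|---|---|---|
| 0.1 | 0.9990 | 0.9982 | 0.9991 | 0.997 |
| 0.2 | 0.9920 | 0.9645 | 0.9723 | 0.918 |
| 0.3 | 0.9730 | 0.8243 | 0.8471 | 0.660 |
| 0.4 | 0.9360 | 0.5637 | 0.6022 | 0.329 |
| 0.5 | 0.8750 | 0.2837 | 0.3242 | 0.105 |
| 0.6 | 0.7840 | 0.0950 | 0.1212 | 0.019 |

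**4. Other readings of the example's condition.**

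- Six new patients with at most 2/6 (for instance at a lower fallback level): at p = 0.3, 0.5797 / 0.7443 = 0.7789; at p = 0.4, 0.2760 / 0.5443 = 0.5070.
- Amendment #1, exactly 2/6: F(3; 10, p) = 0.6496 at 0.3 and 0.3823 at 0.4.
- Amendment #1, exactly 1/6: F(4; 10, p) = 0.8497 at 0.3 and 0.6331 at 0.4.
- Amendment #1, 0/6: F(5; 10, 0.3) = 0.953.

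None gives 0.660 or 0.666 at p = 0.3. The 2/6 route comes close there, but at 0.4 it gives 0.382 against the printed 0.329, so it does not explain the column.

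**The case against.** All twelve table entries are arithmetically right, and the only misprinted number is 66.6%, off by 0.6 points. The last column describes the rule that finally settles the RP2D, and the text promises only some of the operating characteristics. The example speaks of an MTD, which is Amendment #1 language, and does not mention 1200 mg or 0/3, so 0.847 is one reading among several.

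The direction also depends on the reading. Before any data, six new patients pass Table 7 and finish with at most 5/16 with probability 0.580 at p = 0.3 and 0.276 at 0.4, both slightly below the printed column. Finally, nobody can act on an escalation figure when no escalation is possible.

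Much of this stands. The last column should be kept, the misprint alone is minor, and 0.847 depends on using the observed 0/3. But that result is reported in the protocol, and Table 7 is built on it, since each of its rows pairs a count in 3 with the same count in 6. An escalation probability is not a property of the current design under any reading. The example's condition is in the text, and no interpretation of it yields the number printed.

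**Conclusion.** The concern holds. The escalation column and the 31% example belong to superseded rules, and the Table 7 gate has no stated operating characteristic. The example at p = 0.3 is wrong as worded. It quotes an unconditional value, and the conditional value is higher by 0.8471 − 0.6598 = 0.187 for 1200 mg after 0/3, or by 0.7789 − 0.6598 = 0.119 for six new patients.

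The practical gap lies at higher rates. After 0/3, the probability that 1200 mg passes Table 7 and finishes with at most 5/16 is 0.564 at p = 0.4 and 0.284 at p = 0.5, against 0.329 and 0.105 in the only final-rule column. These figures assume independent DLTs with a common rate, 16 evaluable patients, and conditioning on the reported 0/3. The decision rules themselves are not in question here. This should be fixed because the table supports the primary endpoint.

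**What to change.** In Section 5.1.3:

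- Delete the escalation column and the 31% example, or label both as historical.
- Add, for 1200 mg given 0/3, the probability of passing Table 7 and the probability of at most 5/16 given a pass, with the condition in each column header. The joint probability is a useful third column.
- Keep the existing last column and label it unconditional.
- In the example at 0.3, either drop the clause about selection as MTD and quote 0.660, or name the condition (Table 7 passed at 1200 mg after 0/3) and quote 0.847.

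The cost is one table and a few sentences. No decision rule, dose, sample size or endpoint changes. The stated figures for keeping an over-toxic dose will look less favourable than those now printed.

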1.2 Secondary Objectives

1.2.1 To observe and record anti-tumor activity to IPdR-mediated radiosensitization. Although the clinical benefit of this drug used before and during radiation therapy has not yet been established, the intent of offering this treatment is to provide a possible therapeutic benefit, and thus the patient will be carefully monitored for tumor response at 6 months using RECIST criteria in addition to safety and tolerability. Only patients in Part 2 of the study will be included in this evaluation.

1.2.2 To estimate 6 month intracranial progression-free survival (PFS) in brain metastasis cancer patients who receive daily oral IPdR x 28 days and WBRT.

1.2.3 To establish the pharmacokinetics of daily oral dosing of IPdR times 8 days.

1.2.4 To evaluate safety and tolerability of oral IPdR x 28 days and WBRT.

1.2.5 To estimate the incidence of delayed neurological toxicity at 2, 4 and 6 months (\pm 1 week) post-completion of WBRT (for patients without intracranial progression) including:

- Delayed-recall through HVLT-R
- Quality of life as measured by the FACT-BR.

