5.1.4.7 Radiation Adverse Events

A focused history and physical examination should be performed at least once weekly during Weeks 1 through 4 (study treatment) and then towards the end of week 6 and 8 (observation period) to assess for acute treatment-related toxicity.

Acute (\leq 90 days from treatment start): Expected adverse events include hair loss, erythema of the scalp, headache, nausea and vomiting, eye/ear irritation, mucositis, taste/salivary changes, loss of appetite, fatigue, lethargy, and transient worsening of neurological deficits.

Late ($>$ 90 days from treatment start): Possible adverse events include radiation necrosis, cognitive dysfunction, visual difficulties, accelerated atherosclerosis, and radiation-induced neoplasms.

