13.4.4 Intracranial progression free survival (icPFS) and Overall Survival (OS)

These will be explored using the Kaplan-Meier method. For estimation of icPFS, patients alive without intracranial progression at last follow-up will be censored at the date of the last radiologic assessment whereas intracranial progression or death will be scored as events. The icPFS estimates at 6 months with their standard error of the estimate will be reported. For calculation of OS, patients alive at last follow-up will be censored.

13.4.5 Incidence of delayed neurological toxicity at 2, 4 and 6-months (\pm 1 week) post-completion of WBRT (for patients without intracranial progression) including:

- a. Delayed-recall through HVLT-R**
- b. Quality of life as measured by the FACT-BR**

REFERENCES

1. Posner, J.B. and N.L. Chernik, Intracranial metastases from systemic cancer. *Adv Neurol*, 1978. 19: p. 579-92.
2. Stewart, B.W., P. Kleihues, and I.A.f.R.o. Cancer, *World cancer report*. Vol. 57. 2003: IARC press Lyon.
3. Gaspar, L.E., et al., Validation of the RTOG recursive partitioning analysis (RPA) classification for brain metastases. *Int J Radiat Oncol Biol Phys*, 2000. 47(4): p. 1001-6.
4. Nussbaum, E.S., et al., Brain metastases. Histology, multiplicity, surgery, and survival. *Cancer*, 1996. 78(8): p. 1781-8.
5. Sperduto, P.W., et al., Summary report on the graded prognostic assessment: an accurate and facile diagnosis-specific tool to estimate survival for patients with brain metastases. *J Clin Oncol*, 2012. 30(4): p. 419-25.
6. Tsao, M.N., et al., Whole brain radiotherapy for the treatment of newly diagnosed multiple brain metastases. *Cochrane Database Syst Rev*, 2012. 4: p. CD003869.
7. Young, D.F., et al., Rapid-course radiation therapy of cerebral metastases: results and complications. *Cancer*, 1974. 34(4): p. 1069-76.
8. Rades, D., et al., Dose escalation beyond 30 grays in 10 fractions for patients with multiple brain metastases. *Cancer*, 2007. 110(6): p. 1345-50.
9. Chao, J.H., R. Phillips, and J.J. Nickson, Roentgen-ray therapy of cerebral metastases. *Cancer*, 1954. 7(4): p. 682-9.
10. Gaspar, L.E., et al., The role of whole brain radiation therapy in the management of newly diagnosed brain metastases: a systematic review and evidence-based clinical practice guideline. *J Neurooncol*, 2010. 96(1): p. 17-32.

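### Section 5.1.3 limits the late-toxicity endpoint and DSMB review set to undefined 'unexpected' events, its own >20% trigger has no such limit, and section 13.4 analyses no graded late events

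*Combined protocol and SAP*

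**What the plan says.** Two consecutive sentences in section 5.1.3 deal with late toxicity. The first creates the endpoint: "Unexpected severe late neurologic radiation toxicity or extra-cranial radiation toxicity will be recorded as a secondary end-point". The second gives the DSMB its task: "These events will be reviewed by the independent DSMB who will be charged with considering cessation of the trial". It then states the condition, a six-month rate above 20%. The class of event named there is grade 3 or higher: "grade 3 symptomatic neurotoxicity or other extra-cranial radiation toxicity is". *Unexpected* does not appear in that condition.

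Section 5.2 uses the word again. It assigns any grade 3 or higher event from later radiosurgery, stereotactic or fractionated boost, or neurosurgery to unexpected severe late radiation toxicity and to the secondary endpoint, whatever the type of event.

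Section 5.1.4.7 lists what late radiation may cause, more than 90 days from treatment start: "Possible adverse events include radiation necrosis, cognitive dysfunction, visual difficulties, accelerated atherosclerosis, and radiation-induced neoplasms".

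Objective 1.2.5 is differently worded: "To estimate the incidence of delayed neurological toxicity at 2, 4 and 6 months". Section 13.4.5 repeats it, "Incidence of delayed neurological toxicity at 2, 4 and 6-months", restricted to patients without intracranial progression, and names two components, HVLT-R delayed recall and FACT-BR. It gives no grade, cut-off or method. No other entry in 13.4 covers graded late events.

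**The concern.** IPdR is given to sensitise tissue to radiation, so the known late effects of brain irradiation are the safety signal one would look for first. An endpoint confined to unexpected events may pass over exactly those. The DLT rules do not make up for this: DLT is assessed at Day 35 (sections 5.1 and 10), while late effects are defined as starting after 90 days. The 5.1.3 sentence is the only late-toxicity trigger I find in the document, and section 12.1 on oversight does not mention a DSMB. If the events put before the DSMB are a narrower class than the events its threshold names, two careful readers can count the same case of necrosis differently, and nothing elsewhere in the plan settles which of them is right.

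**Working it through.** **Step 1. Set the definitions side by side.**

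| Place | Event class | Limited to *unexpected*? | Grade |
|---|---|---|---|
| 5.1.3, secondary endpoint | late neurologic or extra-cranial radiation toxicity | yes, undefined | severe, undefined |
| 5.1.3, DSMB review set | refers back to the endpoint events | yes, by back-reference | as above |
| 5.1.3, >20% trigger | symptomatic neurotoxicity or other extra-cranial radiation toxicity, six months | no | 3 or higher |
| 5.2, events after later local treatment | any type | labelled so regardless of type | 3 or higher |
| 13.4.5 and 1.2.5 | delayed neurological toxicity, with HVLT-R and FACT-BR as named components | no | none |

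**Step 2. Follow one event through.** Take a grade 3 symptomatic radiation necrosis.
- If it is ascribed to later radiosurgery, 5.2 places it in the endpoint automatically.
- If it is ascribed to IPdR plus WBRT, it enters the endpoint and the DSMB review set only if someone judges it unexpected, although 5.1.4.7 names it in advance.
- In both cases it fits the wording of the trigger.
- In neither case does 13.4 say how it is summarised.

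**Step 3. Look for a figure to reproduce.** The 20% limit has no stated derivation, denominator or error rate. The operating-characteristics table in 5.1.3 concerns DLTs. All 12 of its entries reproduce (for example, P(X ≤ 5 of 16) = 0.660 at a DLT rate of 0.3), but it says nothing about late events.

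**Step 4. Illustrate what the counted share does to the trigger.** Let n be the denominator, r the smallest count above 20% of n, p the true six-month rate and f the share of true events that is counted. Then

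P(trigger) = 1 − Σ_{k<r} C(n,k)(pf)^k(1−pf)^(n−k).

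Possible values of n from the documents are 10 (expansion cohort), 16 (all patients at the RP2D, 5.1.3), and 19 or 25 (range of total accrual, 13.2). Neither p nor f is given anywhere; both are assumed.

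For n = 16, r = 4 (4/16 = 25%) and p = 0.30:
- f = 1: 1 − (0.0033 + 0.0228 + 0.0732 + 0.1465) = 0.754.
- f = 0.5, so pf = 0.15: 1 − (0.0743 + 0.2097 + 0.2775 + 0.2285) = 0.210.

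All denominators at p = 0.30:

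| n | r | f = 1 | f = 0.75 | f = 0.5 | f = 0.25 |
|---|---|---|---|---|---|
| 10 | 3 | 0.617 | 0.398 | 0.180 | 0.034 |
| 16 | 4 | 0.754 | 0.501 | 0.210 | 0.028 |
| 19 | 4 | 0.867 | 0.648 | 0.316 | 0.049 |
| 25 | 6 | 0.807 | 0.506 | 0.162 | 0.009 |

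At p = 0.40 and n = 16 the row reads 0.935, 0.754, 0.402, 0.068. The direction is the same for every denominator; the size depends on the assumptions.

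**The case against.** The case against is substantial, and most of it narrows the point.

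- **The trigger itself is unrestricted.** A reader might infer that listed effects are shut out of the late stopping rule. The condition does not say so; grade 3 or higher symptomatic necrosis meets it. The restriction comes in only through the back-reference that opens the sentence.
- **Listed is not the same as expected.** Section 5.1.4.7 uses *expected* for the acute list ("Expected adverse events include hair loss, erythema of the scalp, headache, nausea and vomiting") and calls the late effects possible. Section 5.2 applies *unexpected* loosely. Exclusion of listed effects is therefore one reading, not a stated rule.
- **The events are still captured.** A reader might infer that they go unrecorded. Section 7.4 requires all adverse events to be reported, the calendar in section 10 collects them at follow-up, section 11.1.1 makes every treated patient evaluable for toxicity, and objective 1.2.4 covers safety without restriction. Section 7.3.3 also requires expedited reports of serious grade 3 to 5 events more than 30 days after the last dose when they are at least possibly related.
- **Section 13.4.5 does not redefine severe toxicity.** A reader might infer that it replaces clinical events with HVLT-R and FACT-BR change. It concerns delayed, not severe, toxicity, and presents the two instruments as components: "post-completion of WBRT (for patients without intracranial progression) including".
- **The illustration is hypothetical.** It also treats every patient as assessable at six months, whereas section 2.1 cites median survivals of 2.3 to 7.1 months by RPA class, and it does not separate out extra-cranial toxicity, which counts toward the trigger.

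All five stand. None of them defines *unexpected*, aligns the review set with the trigger, or supplies an analysis of graded late events. Being in the adverse-event database is not the same as being in the endpoint or in the events the DSMB is asked to weigh.

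**Conclusion.** The point holds as an unreconciled definition. The secondary endpoint and the DSMB review set are tied to an undefined class, the trigger in the DSMB sentence names a wider one, section 5.2 uses the class name in yet another way, and section 13.4 analyses graded late events nowhere. On a literal reading, foreseeable late effects may be omitted from the endpoint and the review set. The documents do not support saying that such events would be unrecorded or that they fall outside the trigger.

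No size can be derived. The fall from 75% to 21% rests on an assumed true rate of 30%, an assumed counted share of one half, a denominator of 16 that the rule does not state, and full six-month assessability. It shows why the definition matters and should not be quoted as an effect. The passages should be reconciled because the remedy is small and this is the only late-toxicity trigger found.

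**What to change.** - In 5.1.3 and 5.2, delete *unexpected*, so that the secondary endpoint and the DSMB review set are the events the trigger already names: grade 3 or higher symptomatic neurotoxicity or other extra-cranial radiation toxicity.
- State that this includes the effects listed in 5.1.4.7, and keep the events from later local treatment that 5.2 already assigns to the endpoint.
- Add one line to 13.4 reporting the number and proportion of patients with such events, with the denominator stated, separately from HVLT-R and FACT-BR. The denominator matters: exceeding 20% takes 4 of 16, 4 of 19 or 6 of 25.

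The change should not be made by writing a single definition confined to neurologic events attributable to IPdR or WBRT. That would drop extra-cranial radiation toxicity, could drop the 5.2 events, and would add an attribution limit that the trigger lacks. The 20% threshold is left as it is.

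The cost is wording in three sections and no new data collection, since adverse events are already collected at follow-up. The reported late-toxicity rate may be less favourable.
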